Appendix 1. Study Variables

Variable	Use, comments, questions
Age	*
Sex	*
Race/ethnicity (white, Asian, black, Latino, Native American, unknown/other)	*
Marital status	
Employment	
Comorbidities	Quan index *
Mental health diagnoses	From MHRN list
Substance use diagnoses	From MHRN list
Number of address changes in last 12 months	New variable – created for [name]’s project
Number of telephone contact # changes in last 12 months	New variable – created for [name]’s project
Number of insurance plan changes in last 12 months	New variable – used by [name]
Clinic site	*Franklin, Lone Tree, Rock Creek
Day of week of appointment	
Exact time of day of appointment	
Health insurance type	*
Duration of enrollment in KPCO	
New member in KPCO	Individuals enrolled < 12 months will be defined as “new enrollees.” May conduct separate subgroup analysis for these individuals. [name] notes that several “segments” of new members have been defined for onboarding interventions.
Appointment lead time	* Exclude if <10 days
Number and rate of ED visits in prior 12 months	*
Number and rate of hospitalizations in prior 12 months	*
Number and rate of missed primary care appointments in prior 12 months	* We will consider various way of analyzing prior missed appointments: a) one or more b) relative risk for each additional missed visit

Number and rate of missed specialty care appointments in prior 12 months	*
Number and rate of missed GI endoscopy appointments in prior 12 months	
Appointment outcome (missed, kept, cancelled)	*
Bowel prep adequacy	Boston Bowel Prep scale (0-9 scale from GI smart set)
Applied for or received medical-financial assistance in last year	New variable – any IHR experience with this? [name] has a contact in KPNW who has extracted this variable UCDA also says that this is accessible.
Unpaid account balance	New variable – how to define?
Geo-located residence	We will use census tract as the primary unit of analysis
Distance from residence to clinic	
Picked up prep kit from KP Pharmacy	Prep kits provided by prescription only; may be picked up from non-KP pharmacies.

Notes:

1. include missing as a category for each variable
2. *= significant variable in prior predictive model(s) in primary care
3. For members with <12 months of enrollment, we will assess utilization from the beginning of enrollment to the date of the first scheduled primary care appointment.

Refs:

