Operational leaders then proposed refinements to the IVR-T approach. We designed a 3-armed randomized trial in all KPCO primary care clinics comparing a single IVR-T reminder one day prior to a primary care visit, a single reminder 3 days prior to the visit, and two reminders, delivered both 1 and 3 days prior to the visit. In addition, we assessed the effect of the intervention in all primary care sites on visit satisfaction. This trial was conducted between October and December 2016. In this study, reminders both 1 and 3 days prior to a visit reduced missed appointments by 1.4% (absolute percentage) compared to a 3-day reminder, and by 0.9% compared to a 1-day reminder alone ($p<0.001$ for both comparisons). The effectiveness of 2 reminders was particularly strong in individuals who were at predicted high risk of missing appointments. For these individuals, 2 reminders reduced missed appointments by 4.5% and 3.7%, respectively. Based on these findings, 3-day and 1-day IVR-T reminders are now standard for all primary care visits in KPCO.

Clinical and operational leaders have now requested the IHR develop IVR-T interventions to reduce missed GI endoscopy procedures in KPCO. GI endoscopies (both upper and lower endoscopy) are performed at Franklin, Rock Creek, and Lone Tree facilities. GI clinic managers have tracked “appointment loss,” defined as prior-day cancellations, same-day cancellations, or missed visits since 2013. The trends over this period are shown in Table 1:

Table 1: Appointment Loss in GI Procedure Clinics, KPCO, 2013-2018

Site	2013	2014	2015	2016 (January-May)	2017	2018 (January- mid-October)
Franklin	8.7%	9.6%	8.8%	9.6%	x	Total = 9.2% No show – 2.5% Same-day cancel – 2.6% Prior day cancel – 4.1% N = 7612
Rock Creek	6.4%	6.4%	5.3%	5.9%	x	Total = 4.8% No show – 1.2% Same-day cancel – 1.2% Prior day cancel – 2.4% N = 7592
Lone Tree	6.0%	7.4%	5.2%	6.5%	x	Total = 6.5% No show – 1.2% Same-day cancel – 1.0% Prior day cancel – 3.2% N = 9283

These rates have been relatively constant over time. They represent substantial inefficiency for the KPCO system and prevent many members from receiving their procedure in a timely way. Each unfilled slot represents an estimated cost of about \$1200 to KPCO.

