- For the duration of this intervention, the GI clinic will discontinue all live pre-procedure reminders so that we can assess the effectiveness of a purely automated intervention. Staff will continue post-procedure calls to assess service quality. Selective live reminders for members at high risk of missed appointments will be assessed in Step 3 of this project.

Intervention delivery: All interventions by email, text and telephone will be delivered by secure messages from the Automated Communication Technology (ACT) team in the KPCO

Institute for Health Research. At present, GI clinic nurses or staff make live reminder calls to some members as time allows; these calls will be stopped for the duration of the Step 1 trial.

Over the 6-month period of the project, we estimate that approximately 2300 visits per month will be scheduled across the 3 participating sites. After anticipated exclusions (10% of total cases), we estimate that there will be approximately 2100 eligible appointments per month. We project that the study will run from March 8, 2019 through September 7, 2019 to achieve the proposed sample size of approximately 13,000 appointments. The duration of the study will be dictated by the number of appointments necessary to detect an operationally significant reduction in the rate of appointment loss, as described in the sample size calculations below. We will monitor recruitment during the study and adjust the duration of the randomization period as necessary to achieve the projected sample size.

9. Study Measures

Outcome variable: The primary outcome for the study will be “appointment loss”, defined by GI leaders as the combined rate of prior day cancellations, same-day cancellations, and missed clinic appointments (“no shows”). The rationale for this outcome definition is that it is difficult to schedule new procedures within this time frame. As a secondary outcome, we will assess the adequacy of the bowel preparation for colonoscopy only.

Covariates: To describe the project participants and identify clinically and operationally relevant subgroups, we will measure patient covariates that we have used in prior IVR-T evaluations in primary care clinics, as well as variables specific to the GI clinic setting. These variables are listed in Appendix 1. All variables will be drawn from the IHR Virtual Data Warehouse (VDW), KPCO appointment scheduling system, or endoscopy data from Clarity.

10. Sample size and statistical analysis

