Sample size calculation: As shown in Table 1, “appointment loss” in the 3 GI clinics has been 6.8% from January – mid-October 2018. Across sites, approximately 2580 procedures/month were scheduled, and 175 were missed. Using standard parameters for Type 1 error (0.05, two-sided) and Type 2 error (0.20), the necessary sample to detect differences between standard and enhanced IVR-T protocols is:

Table 3. Sample Size Estimates

Detectable difference in appointment loss	N total (per group)	Duration of project (months)
3% absolute difference (6.8% vs. 3.8%)	2654 (1327)	1.3
2% absolute difference (6.8% vs. 4.8%)	5644 (2822)	2.7
1% absolute difference (6.8% vs. 5.8%)	21244 (10622)	10.1
20% relative difference*	11112 (5556)	5.3

(6.8% vs. 5.4%)		
-----------------	--	--

*Effect consistent with prior KPCO trials and systematic reviews of missed appointment interventions

Based on these calculations, a 6-month study will provide statistical power to detect a 20% relative difference in appointment loss.

Analytic plan Statistical analyses will be consistent with approaches used in prior IVR-T interventions. Patient demographic and clinical characteristics will be compared between the 2 groups using *t*-tests for normally distributed continuous variables, Wilcoxon rank tests for non-normally distributed continuous variables, and chi-square tests for discrete variables. We will assess the effectiveness of the intervention across the 3 participating clinics, after adjusting for predictors of missed appointments/late cancellations. To estimate the number of additional kept visits and available appointments per week that would result if the most effective intervention were implemented for all visits that met inclusion criteria, we will multiply the average number of visits at each clinic by the sum of the rate reduction in missed appointments and the rate increase in cancelled appointments at that clinic.

We will conduct three planned subgroup analyses:

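### The risk model for the quartile subgroup analysis is offered no history of late cancellation, although late cancellation makes up about three quarters of the outcome it predicts

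*Combined protocol and SAP*

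**What the plan says.** Section 9 (Study Measures) defines the primary outcome as "the combined rate of prior day cancellations, same-day cancellations, and missed clinic appointments". In section 10, the first planned subgroup analysis builds a multivariable logistic model for that composite. Clinic site is a fixed effect and predictors are chosen by backward selection with Wald tests. The fitted rule then divides participants into risk quartiles, and the effect of the intervention is assessed in each.

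Appendix 1 lists the variables. Three rows describe a member's own appointment history: missed primary care visits, "Number and rate of missed specialty care appointments in prior 12 months", and the corresponding row for GI endoscopy. The first two are starred as significant in the earlier primary care models; the GI row is not. No row covers prior cancellations. The appendix has a separate row for the appointment outcome, which treats missed, kept and cancelled as three different results.

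Table 1 gives the make-up of appointment loss by site for January to mid-October 2018.

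**The concern.** The plan treats past appointment behaviour as worth modelling, but only for no-shows, which are the smaller part of this outcome. Backward selection can drop a weak candidate; it cannot keep one that was never offered. If members who have cancelled late before tend to do so again, leaving that history out makes the risk score less discriminating and brings the quartiles closer together.

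The ranking has a practical use. The background reports that two reminders worked particularly well in members at high predicted risk of missing primary care visits. The intervention section says that selective live reminders for high-risk members will be assessed in a later step of the project. A score that separates risk less well gives a weaker basis for both questions.

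**Working it through.** **1. Reproduce the plan's overall rate.** The inputs are the Table 1 entries for 2018:

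- Franklin: "Total = 9.2% No show – 2.5% Same-day cancel – 2.6% Prior day cancel – 4.1% N = 7612"
- Rock Creek: "Total = 4.8% No show – 1.2% Same-day cancel – 1.2% Prior day cancel – 2.4% N = 7592"
- Lone Tree: "Total = 6.5% No show – 1.2% Same-day cancel – 1.0% Prior day cancel – 3.2% N = 9283"

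Total appointments = 7612 + 7592 + 9283 = 24,487. Expected losses = 7612 × 0.092 + 7592 × 0.048 + 9283 × 0.065 = 700.3 + 364.4 + 603.4 = 1668.1. The rate is 1668.1 / 24,487 = 6.81%, which agrees with the 6.8% used in the sample size section.

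**2. Split the outcome.**

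| Component | Franklin | Rock Creek | Lone Tree | All | % of visits |
|---|---|---|---|---|---|
| No-show | 190.3 | 91.1 | 111.4 | 392.8 | 1.60 |
| Same-day cancellation | 197.9 | 91.1 | 92.8 | 381.8 | 1.56 |
| Prior-day cancellation | 312.1 | 182.2 | 297.1 | 791.4 | 3.23 |

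Late cancellations are 381.8 + 791.4 = 1173.2, or 4.79% of visits. The Lone Tree components add to 5.4% against a stated total of 6.5%, so the share depends on where the missing 1.1 points belong:

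- Components as printed: 1173.2 / 1566.0 = 74.9%.
- Gap counted entirely as cancellation: (1668.1 − 392.8) / 1668.1 = 76.45%.
- Gap counted entirely as no-show: 1173.2 / 1668.1 = 70.3%.

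Late cancellation is the larger part at every site: 72.8%, 75.0% and 77.8% of the printed components at Franklin, Rock Creek and Lone Tree.

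**3. Count the candidates.** Appendix 1 has 30 rows. Two are outcomes (appointment outcome and bowel prep adequacy), which leaves 28. Three are missed-visit history, 25 are other characteristics, and none is cancellation history.

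**4. What fitting to the composite does to a no-show marker.** Suppose a history marker multiplies no-show risk by R, leaves cancellation risk unchanged and is present in a fraction f of members. No-show risk without the marker is b = 1.604% / (1 + f(R − 1)). The composite risk ratio is (R·b + 4.791%) / (b + 4.791%).

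- R = 2, f = 0.1: b = 1.458%, ratio = 7.707 / 6.249 = 1.23.
- R = 2, f = 0.2: b = 1.337%, ratio = 7.465 / 6.128 = 1.22.
- R = 3 gives 1.44 and 1.39.

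A predictor of no-shows alone is thus down-weighted by the fit.

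**5. What the omitted history could add.** The documents give neither the prevalence nor the strength of this predictor, so both are assumed. The other predictors are represented by a normal score with SD 0.75 on the logit scale, which gives c of about 0.70. That is the validation value the literature review quotes for the one published rule. The overall loss rate is 6.8%. A binary prior-late-cancellation indicator, independent of the score, is then added.

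| Adjusted odds ratio | Prevalence | Rise in c | Top-quartile share of losses, without → with |
|---|---|---|---|
| 1.5 | 10% | 0.003 | 50.1% → 50.5% |
| 1.5 | 20% | 0.005 | 50.0% → 50.7% |
| 2 | 10% | 0.009 | 50.0% → 51.3% |
| 2 | 20% | 0.015 | 49.9% → 52.1% |
| 3 | 10% | 0.023 | 49.7% → 53.4% |
| 3 | 20% | 0.037 | 49.5% → 55.5% |

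**The case against.** A reader might infer that the quartiles rest mainly on no-shows, the smaller part of the outcome. The documents do not support that. The model is fitted to the whole composite, so every coefficient is estimated against cancellations as well as no-shows, and step 4 shows how this shrinks a predictor of no-shows alone. Most candidates have nothing to do with missed visits: lead time, insurance, comorbidity, mental health and substance use diagnoses, acute care use, distance and prep kit pick-up are all offered. No coefficients are given, so dominance by the three history rows cannot be shown.

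It can also be said that the literature review, which covers predictors of missed or cancelled appointments, names prior missed visits and not prior cancellations. The list was adapted for this setting, since the GI endoscopy row is not starred as a primary care predictor. Both statements are correct. They mean that the value of cancellation history is plausible but not demonstrated, and offering it as a candidate is how to find out.

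The word missed is not used consistently. The sample size section calls all 175 monthly losses missed, so the GI history row could be meant to include late cancellations. The three-way outcome row in the same appendix points the other way. Either reading calls for a definition.

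Finally, the documents do not show that prior-day and same-day timing can be retrieved for primary and specialty care. GI leaders chose that window because endoscopy slots are hard to refill, and its relevance elsewhere is assumed. This stands, and it limits the fix.

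**Conclusion.** The omission is real and its effect is probably modest. About 75% of the modelled outcome (70% to 76%) is late cancellation, and Appendix 1 offers no history of it. Under assumed odds ratios of 1.5 to 2 and prevalences of 10% to 20%, c rises by about 0.003 to 0.015. The top quartile's share of losses rises by 0.4 to 2.2 points. Only an adjusted odds ratio near 3 would give more, and that value would have to hold after adjustment for the other predictors. If only GI history is used and it is present in fewer than 10% of members, the gain falls below these figures.

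The point concerns one subgroup analysis. Randomised contrasts within quartiles stay valid with a somewhat less discriminating score, the primary comparison is untouched, and the planned c-statistic would make weak discrimination visible. This is an inexpensive improvement to the plan and not a flaw in the trial.

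**What to change.** Add to Appendix 1, as candidate predictors, the number and rate of late cancellations (prior-day and same-day combined) in the prior 12 months. Do this for GI endoscopy at minimum. Add primary and specialty care only if cancellation timing proves retrievable there. State in the appendix that missed means no-show in the history rows.

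For GI visits the cost is a longer look-back on information that the primary outcome already requires. Number and rate for GI alone add 2 candidates, and all three settings add 6. Keeping the two cancellation types separate would double that to 12, which is why they are better combined. For scale, 13,000 appointments split equally, with loss of 6.8% and 5.4% as in the plan's 20% relative scenario, give 6500 × 0.068 + 6500 × 0.054 = 442 + 351 = 793 events. Restricting the analysis to first appointments would lower this somewhat. A few extra candidates are a light burden at that size, and backward selection can remove them if they are uninformative.

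### The plan does not limit model covariates to values known at randomization, and Appendix 1 lists prep-kit pick-up without a time window; the possible dilution of the adjusted effect is conditional and probably small

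*Combined protocol and SAP*

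**What the plan says.** Section 9 (Study Measures, Covariates) says the trial will use covariates from the earlier primary care evaluations "as well as variables specific to the GI clinic setting", and adds: "These variables are listed in Appendix 1". The stated purpose is "To describe the project participants and identify clinically and operationally relevant subgroups".

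Appendix 1 is a mixed list. It contains the primary outcome ("Appointment outcome (missed, kept, cancelled") and the secondary outcome ("Boston Bowel Prep scale (0-9 scale from GI smart set") alongside demographic, utilization and scheduling variables. It also contains "Picked up prep kit from KP Pharmacy". The comment on that row covers only the prescription requirement and the possibility of collection at a non-KP pharmacy. The row has no time window, whereas many utilization and contact-change rows look back 12 months. It carries no star; Note 2 defines a star as "significant variable in prior predictive model(s) in primary care".

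Section 10 (Analytic plan) assesses effectiveness "after adjusting for predictors of missed appointments/late cancellations" without naming the predictors. It describes no unadjusted overall comparison. Planned subgroup analysis 1 selects predictors backward by Wald tests, keeps those with p<0.05 together with a treatment indicator, and uses the resulting rule to form risk quartiles in which the effect is assessed. No section says that candidate predictors must be known at randomization.

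**The concern.** Collecting a prep kit is something a member does between booking and procedure, so it can happen after reminders have started. The arms differ in what they receive over that time. The enhanced arm gets more reminders, through more channels, with motivational content. Standard-arm members who book within 7 days get no reminder (Intervention content). Pick-up could therefore respond to the assigned arm.

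It is also plausibly a strong correlate of attendance, since a member who has decided not to come has little reason to fetch the kit. Selection by p-value would then tend to keep it.

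Adjusting for a consequence of treatment removes from the estimate whatever part of the effect runs through it. A risk score that contains it sorts members partly by how they responded to treatment, so an effect within a quartile is not an effect within a baseline risk group.

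**Working it through.** **1. The plan's own figures.** The documents give no figure for pick-up, so there is none to reproduce on this point. The control rate does reproduce from the 2018 column of Table 1: (7612 × 9.2% + 7592 × 4.8% + 9283 × 6.5%) / 24,487 = 6.8%. The target is the 20% relative row of Table 3, 6.8% vs 5.4%, a difference of 1.40 points. (The 5,556 per group printed there is the number for 6.8% vs 8.2%; 6.8% vs 5.4% needs about 4,587. That is a separate matter and does not affect what follows.)

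**2. Other inputs.**
- From the plan: 2,100 eligible appointments a month × 6 = 12,600, or 6,300 per arm; two-sided 0.05. Unadjusted power for 6.8% vs 5.4% is then 91%.
- Assumed: control pick-up of 85–90%; loss of 15–20% among those who do not collect (22–44% of all loss: 0.10 × 15 / 6.8 to 0.15 × 20 / 6.8); a rise in pick-up of 0, 1 or 2 points in the enhanced arm; the rest of the effect proportional among collectors and non-collectors.

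**3. Formula.** Loss among collectors = (6.8 − share not collecting × loss without kit) / share collecting. Points removed ≈ rise in pick-up × gap in loss between non-collectors and collectors.
- Low end (90%, 15%): (6.8 − 1.5) / 0.90 = 5.9%. The gap is 9.1 points, so a 1-point rise removes about 0.09.
- High end (85%, 20%): (6.8 − 3.0) / 0.85 = 4.5%. The gap is 15.5 points, so a 2-point rise removes about 0.31.

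**4. Adjusted results.** These use expected cell counts, the Mantel-Haenszel risk difference over recorded pick-up (a measure chosen here, not by the plan), and Wald power from a logistic model with arm and pick-up.

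| Rise in pick-up | Everyone needs a kit, perfect recording | 10% of pick-ups non-KP, 20% upper endoscopy |
|---|---|---|
| 0 | 1.40 points, power 91–92% | no attenuation |
| 1 point | 1.26–1.32 points, power 85–87% | 1.34–1.38 points, power 88–90% |
| 2 points | 1.11–1.23 points, power 76–83% | 1.27–1.37 points, power 85–89% |

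Both categories in the last column come from the documents (Appendix 1 and Inclusion criteria); the percentages are assumed.

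**5. Quartiles.** Take a 2-point rise, other predictors with a c-statistic of about 0.70, and a score computed without the treatment term. The top quartile then holds 25.5–25.8% of controls and 24.2–24.5% of the enhanced arm, a small imbalance. This departs from the plan, whose final model contains the treatment indicator. If that term stays in the score, the top quartile holds about 30% of controls and 20% of the enhanced arm with no pick-up variable at all. So pick-up is the lesser threat to the quartiles.

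**The case against.** The harm needs four things to happen: pick-up is offered to a model, is retained, is counted after randomization, and is changed by the reminders. The documents show none of them.

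Appendix 1 reads as a working list with open questions, and because it contains both outcomes the analysts must sort it anyway. Most other time-dependent rows already have look-back windows. The existing colonoscopy reminders already carry prep information, and the day-before message concerns starting the prep, not collecting the kit. All of this stands, and it keeps the priority low.

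It does not remove the gap. Pick-up is a listed non-outcome row, the covariates are said to be the listed variables, and the selection rule keeps every covariate that passes p<0.05. The missing star excludes nothing: it records significance in primary care models, where a prep kit would not be expected to appear.

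A reader might infer that the plan commits to adjusting for pick-up, or that the main result will be badly diluted. The documents support neither. Listing a variable is not a modelling instruction, and large losses come only from large assumptions. For example, suppose pick-up rises from 80% to 84% and loss is six times higher without a kit (20.4% vs 3.4%). Non-collectors then account for 0.20 × 20.4 / 6.8 = 60% of all loss, and 0.04 × 17.0 = 0.68 of a 1.36-point effect is routed through pick-up. Half the effect disappears because the inputs say so.

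Barring pick-up altogether would go too far. The plan does not say when in the booking process assignment occurs, so pick-up recorded before randomization would be a legitimate baseline value.

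**Conclusion.** The concern holds as a conditional one. Followed literally, the covariate rule can admit a post-randomization behaviour into the adjusted effect and the risk quartiles, and no sentence prevents it. This is more than missing detail, because the rule itself can bias the result towards no effect.

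The likely size is small: no attenuation if the reminders leave pick-up unchanged, and roughly 0.1 to 0.3 of 1.4 points for a 1- to 2-point rise. It is smaller again once kits collected elsewhere and upper endoscopy are allowed for, where power stays at 85–90%, above the planned 80%. Every pick-up rate behind these figures is an assumption. Priority: minor.

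**What to change.** In the Analytic plan and planned subgroup analysis 1 (section 10), state that covariates for the adjusted effect and for the risk score are limited to values known at or before randomization of the index endoscopy appointment. Remove prep-kit pick-up after randomization from the candidate predictors. It would help to mark each Appendix 1 row as outcome, candidate predictor, or descriptive or process measure. If pick-up is of interest, report it by arm among colonoscopy patients as a process measure, noting that kits collected at non-KP pharmacies may not be captured.

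The cost is a wording change and the loss of one possibly strong predictor from the risk model.

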- Another randomized trial suggests that a live call the day prior to the procedure can increase the adequacy of the bowel prep.

PROJECT QUESTIONS AND HYPOTHESES

This project will address the following question:

Does an “enhanced” IVR-T protocol differ in effectiveness from the standard IVR-T protocol in reducing missed appointments and late cancellations for GI endoscopy?

Hypothesis 1: The enhanced IVR-T protocol will be more effective.

RESEARCH DESIGN AND METHODS

We will conduct a randomized trial over a 6-month period (March through September 2019) in the 3 GI endoscopy clinics (Franklin, Rock Creek, and Lone Tree). All members currently receive a text reminder 7 days prior to their procedure, which rolls over to a telephone reminder if the text cannot be delivered or the member’s phone is not text-enabled. Members will be randomized either to receive this standard IVR-T protocol or to receive an enhanced reminder protocol.

Inclusion criteria:

- a. Members scheduled for any GI procedure (upper endoscopy, colonoscopy, or both), with or without anesthesia, at all three clinical sites (Franklin, Rock Creek, Lone Tree) will be included if their procedure is scheduled \geq 2 days prior to the procedure. The IVR-T protocol will be adapted based on the wait time between appointment scheduling and the date of the procedure.
- b. Members with all clinical indications (screening, diagnosis, or surveillance), will be included.

Exclusion criteria:

- a. KPCO members who request not to participate in research or not to receive IVR-T or email outreach
- b. KPCO members in the “break the glass” or “code pink” protocols.
- c. Members whose procedure is scheduled $<$ 2 days prior to the procedure.

Randomization: Beginning in March 2019 (or on completion of all necessary design steps), we will use the randomization algorithm in the Structured Query Language program that manages the IVR relational database to assign each visit for a procedure at all three sites to one of the two interventions. Since members with multiple procedures on different days during the study period could receive different interventions for different visits, we will limit the statistical analysis to the first randomized appointment during the project period. Randomization will be stratified by clinic site.

Intervention content

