1. We will develop a multivariable logistic regression model to predict appointment loss using approaches similar to prior IVR-T interventions. Clinic site will be included as a fixed effect. We will include linear and quadratic terms for continuous predictors and include both terms in the final model if statistically significant. Missing values for each predictor will be included as a separate category. Backward selection with Wald chi-square tests will guide the selection of predictors. The final prediction model will include an indicator variable for treatment group and all covariates with *p*-values <0.05. The discrimination of the model will be assessed with the *c*-statistic. We will use this prediction rule to stratify participants into risk quartiles and will assess the effectiveness of the intervention in each quartile.
2. We will assess the effectiveness of the intervention in each of the 3 participating clinics, after adjusting for predictors of missed appointments/late cancellations, to provide preliminary information on site-level factors that may modify intervention effectiveness.
3. We will analyze the effectiveness of the intervention in the subgroup of individuals who schedule their endoscopies \leq 7 days prior to the procedure, since these individuals will receive no reminders under the standard protocol.

Human subjects

The standard reminder protocol includes a text message that “rolls over” to an IVR automated phone if the text cannot be delivered. The GI Clinic has received permission from the KPCO Compliance Office to send emails to the private email addresses of KPCO members.

Study Risks: This study utilizes current standard protocols for contacting KPCO members and data collected during the course of routine clinical care to improve efficiencies in the delivery and quality of care for patients. Therefore, the primary risk of this study is the potential for loss of confidentiality and privacy of a member, through a loss or inappropriate disclosure of study data. There are no known risks to investigators or staff.

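### Appendix 1, Note 3 ends the utilization look-back for members enrolled under 12 months at a primary care visit, which is not an event in this endoscopy trial, and so can misstate prior-utilization predictors for some new members

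*Combined protocol and SAP*

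**What the plan says.** Appendix 1 (Study Variables) lists five utilization predictors measured over the preceding year: ED visits, hospitalizations, and missed primary care, specialty care and GI endoscopy appointments. Typical entries are "Number and rate of ED visits in prior 12 months" and "Number and rate of missed primary care appointments in prior 12 months". The appendix does not say on what date that year ends. All but the missed endoscopy entry carry a star, which Note 2 explains as "significant variable in prior predictive model(s) in primary care".

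Note 3 sets a special rule for members with under 12 months of enrollment: "we will assess utilization from the beginning of enrollment to the date of the first scheduled primary care appointment".

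The unit of analysis is defined under Randomization, in Research Design and Methods. Each endoscopy visit is assigned to an arm, and "we will limit the statistical analysis to the first randomized appointment during the project period".

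The predictors are used in two places in section 10. The analytic plan assesses effectiveness after adjustment for predictors of appointment loss. Planned subgroup analysis 1 builds a logistic prediction model by backward selection, then states: "We will use this prediction rule to stratify participants into risk quartiles and will assess the effectiveness of the intervention in each quartile".

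**The concern.** A baseline look-back should end at or before randomization and should be tied to the event being analyzed. Here that event is an endoscopy appointment. Note 3 ties the window to a different kind of visit, whose date has no fixed relation to the endoscopy. It may come before it, after it, or not at all.

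Two things are at stake. The first is risk classification. The background section reports that two reminders worked best in members predicted to be at high risk of missing visits, and section 8 reserves selective live reminders for high-risk members to a later step. The quartile analysis therefore feeds an operational decision, and mis-timed predictors blur it for new members. The second is the adjusted estimate. A covariate that takes in events after randomization is no longer a baseline covariate, and in the extreme case it could contain the outcome itself.

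**Working it through.** The plan states no figure on this point, so there is none to reproduce. The check sets the rule against the design, and then illustrates how often a value would change.

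**Step 1: the rule against the design.** The window opens at enrollment and closes at a primary care visit. The index event is the first randomized endoscopy appointment. No other part of the document links the two dates or corrects Note 3. I take utilization in Note 3 to cover all five predictors listed above.

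**Step 2: the possible orders of events for a new member.**

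- *Primary care visit before the endoscopy.* Events between the two dates are dropped although they precede the endoscopy and would be known.
- *Primary care visit after randomization.* Post-randomization events enter the predictor. If the visit also follows the endoscopy, a missed index endoscopy could be counted as a prior missed endoscopy, so the outcome would help to predict itself.
- *No primary care visit.* The window has no end date.
- *Missed primary care appointments in particular.* If first means first since enrollment, the window closes as the first such visit falls due. The count is then zero, or at most one if the closing date is included, and a rate per scheduled primary care visit has no usable denominator.

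**Step 3: how often a count would change.** Take the case where the primary care visit comes first. Let T be months enrolled at the endoscopy, t the month of the primary care visit, and r the events per year, with events arriving at a constant rate. The chance of at least one event in the omitted stretch is

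P = 1 − exp(−r × (T − t)/12).

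T, t and r are not in the documents. The ranges below are assumptions.

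| T | t | Months omitted | r = 0.1 | r = 0.3 | r = 0.5 | r = 1.0 |
|---|---|---|---|---|---|---|
| 11 | 1 | 10 | 8.0% | 22.1% | 34.1% | 56.5% |
| 11 | 3 | 8 | 6.4% | 18.1% | 28.3% | 48.7% |
| 11 | 6 | 5 | 4.1% | 11.8% | 18.8% | 34.1% |
| 6 | 1 | 5 | 4.1% | 11.8% | 18.8% | 34.1% |
| 6 | 3 | 3 | 2.5% | 7.2% | 11.8% | 22.1% |
| 6 | 6 | 0 | 0% | 0% | 0% | 0% |

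For example, with T = 11, t = 1 and r = 0.3, P = 1 − exp(−0.3 × 10/12) = 1 − exp(−0.25) = 22.1%. The table spans 0% to 57%, and 0% to 22% at r = 0.3. These are shares of such new members for one predictor, with the gap measured to the endoscopy. For these visits, an anchor between the primary care visit and the endoscopy would shorten the gap and lower the shares.

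**Step 4: what is touched.** Only the five utilization predictors are affected. Age, sex, race and ethnicity, comorbidity, insurance, lead time and site are not. The sample size in Table 3 uses two event rates, alpha and power, and does not depend on any covariate.

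**The case against.** The best defense is that this is a leftover term and not a chosen analysis. Section 9 says the covariates include those used in earlier primary care evaluations, where a first scheduled primary care visit may well have been the index visit. The appendix is plainly a working list, with open questions in its comments column. An analyst might replace the old index visit with the new one without being told. That origin is plausible, but it explains the wording without correcting it, and the rule as written is what would be programmed.

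Several safeguards soften the effect. Missing predictor values form their own category, which gives a member with no primary care visit somewhere to go. Each predictor is planned as a number and a rate, which partly allows for a short window. Enrollment duration and a new-member indicator are also listed and, if retained, could absorb an average shift. Backward selection keeps only covariates with p below 0.05, so some of the five may drop out; a star records significance in earlier models, not selection here. These points stand as limits on the size of the problem. None of them restores risk information lost among new members or removes post-randomization events.

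A reader might also go further and infer that the predictors are wrong for every new member. The documents do not support that: the window is mis-stated for all of them, but a value changes only if an event falls in the stretch wrongly omitted or included. Nor do they support a flat statement that prior missed primary care visits are always zero, since that depends on one reading of first. It is also not shown that new members would be pushed towards low predicted risk; the net direction depends on visit timing and on which covariates are retained.

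**Conclusion.** Note 3 is wrong as written. It is a stated rule that does not fit the trial's index event, not merely a missing detail. It can misstate up to five prior-utilization predictors for some members enrolled under 12 months.

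The overall size cannot be fixed from the documents, because the number of new members and the timing of their primary care visits are not given. The 0% to 57% range rests wholly on assumed inputs and describes one predictor among such members, not the trial population.

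The consequences are limited to the prediction model, the risk quartiles and the covariate-adjusted estimate. Covariates that are mis-timed but still precede randomization do not bias the comparison of randomized arms; they weaken risk stratification and precision. Bias is a concern only where the primary care visit falls after randomization, and nothing indicates how often that happens. An unadjusted comparison by arm would be unaffected, although the analytic plan describes its effectiveness analysis as an adjusted one. The correction is worth making because it is nearly free and the error is definite, even though its effect is bounded.

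**What to change.** Rewrite Note 3 so that, for members with less than 12 months of enrollment, the look-back runs from the start of enrollment to one named date tied to the index endoscopy appointment (the first one randomized) and no later than its randomization. The date on which that appointment was booked is a natural choice. The document does not say that booking and randomization fall on the same day, so the chosen date should be named explicitly.

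Use the same end date for the 12-month window in all other members, since Appendix 1 gives none. The cost is one sentence in Appendix 1 and one date field in the data extraction. The design and sample size do not change.
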